12.1.3 Statistical Methods for Observational Objectives

No hypotheses will be tested. Descriptive statistics will be presented.

Immunogenicity

Descriptive analyses on A, C, W, and Y serogroups for all subjects in Group 3 providing a blood sample at corresponding time points (Visit 2, Visit 3, Visit 4, and Visit 5) using hSBA will include but not be limited to:

- GMT and 95% CI
- Percentage of subjects with titer $\geq 1:4$ and $\geq 1:8$ and 95% CI

Descriptive analyses on A, C, W, and Y serogroups for a subset of subjects in Group 3 providing a blood sample at corresponding time points (Visit 2, Visit 3, Visit 4 and Visit 5) using rSBA will include but not be limited to:

- GMT and 95% CI
- Percentage of subjects with titer $\geq 1:8$ and $\geq 1:128$ and 95% CI

Safety

Safety results will be described for subjects in all study groups after vaccination at 2, 3, 4, and 12 to 13 months of age (Visit 1, Visit 2, Visit 3, and Visit 4, respectively). SAEs will be summarized throughout the trial. The main parameters for the safety endpoints will be described by 95% CIs (Clopper-Pearson method).

12.1.4 Sensitivity analysis due to COVID-19 pandemic

The impact of COVID-19 pandemic situation on study conduct will be summarized through impact on visit procedures, study completion and major/critical protocol deviations due to COVID-19. The subjects impacted by COVID-19 pandemic situation will be defined as the subjects with at least one major/critical protocol deviation due to COVID-19 or who did not complete the study due to COVID-19. If more than 10% of subjects are impacted as per this definition, the main immunogenicity and safety endpoints will also be summarized in these subjects to assess the impact of COVID-19 situation on study outcome.

12.2 Analysis Sets

All immunogenicity analyses will be performed on the PPAS. Additional immunogenicity analyses will be performed for exploratory purposes on the Full Analysis Set (FAS) according to the randomization group. All safety analyses will be performed on the Safety Analysis Set (SafAS).

The study vaccines refer to MenACYW conjugate vaccine, Bexsero[®] vaccine and concomitant routine vaccines in the pre-defined vaccination schedule from Visit 1 to Visit 4.

The investigational product only refers to MenACYW conjugate vaccine or Bexsero[®] vaccine.

12.2.1 Full Analysis Set

There will be 3 Full Analysis Sets (FASs) for this study. Immunogenicity analyses will be performed on the 3 FASs for exploratory purposes.

12.2.1.1 Full Analysis Set 1 (FAS1) for Infant Vaccination (< 12 Months of Age):

The FAS1 is defined as the subset of all randomized subjects who received at least 1 dose of the study vaccine in infancy (at Visit 1 to Visit 3, <12 months of age), and have a valid post-vaccination serology result at Visit 3 in infancy. All subjects will be analyzed according to the treatment group to which they were randomized.

12.2.1.2 Full Analysis Set 2 (FAS2) for Persistence after Infant Vaccination (< 12 Months of Age):

The FAS2 is defined as the subset of all randomized subjects who received at least 1 dose of the study vaccine in infancy (at Visit 1 to Visit 3, <12 months of age), and have a valid post-vaccination serology result at Visit 4 (12 to 13 months of age). All subjects will be analyzed according to the treatment group to which they were randomized.

12.2.1.3 Full Analysis Set 3 (FAS3) for Second Year of Life Vaccination (12 to 13 Months of Age):

The FAS3 is defined as the subset of all randomized subjects who received at least 1 dose of the study vaccines at Visit 4 (12 to 13 month of age) in the second year of life, and have a valid post-vaccination serology result at Visit 5 in the second year of life (13 to 14 months of age). All subjects will be analyzed according to the treatment group to which they were randomized.

12.2.2 Safety Analysis Set

The Safety Analysis Set (SafAS) is defined as those subjects who have received at least one dose of the study vaccine(s)^a and have any safety data available. Specific safety analysis will be defined and used after each vaccination. All subjects will have their safety analyzed after each dose according to the vaccine they actually received at each visit, and after any dose according to the vaccine received through Visit 1 to Visit 4.

Safety data recorded for a vaccine received out of the protocol design will be excluded from the analysis (and listed separately).

There will be five SafASs for this study.

^a for which safety data are scheduled to be collected

12.2.2.1 Overall Safety Analysis Set for Any Dose (SafAS)

The overall SafAS is defined as those subjects who have received at least one dose of the study vaccine and have any safety data available.

All subjects will have their safety analyzed after any dose according to the vaccine received from Visit 1 (2 months) to Visit 4 (12 through 13 months).

- 1) If one subject received both MenACYW conjugate vaccine and Bexsero[®] vaccine at Visit 4, the actual vaccination group is “Group 1”.
- 2) Else if one subject only completed Visit 1 and received Bexsero[®] at Visit 1, the actual vaccination group will be classified as “Group 1”, “Group 2” or “Group 3” according to the randomization group.
- 3) Else if one subject did not receive both MenACYW conjugate vaccine and Bexsero[®] vaccine at Visit 4, but received at least one dose of MenACYW from Visit 1 to Visit 4, the actual vaccination group is either “Group 1” or “Group 2” based on the randomization group.
- 4) Else if one subject did not receive MenACYW conjugate vaccine but received at least one dose of Bexsero[®] vaccine from Visit 1 to Visit 4, the actual vaccination group is “Group 3”.
- 5) Else if one subject did not receive MenACYW conjugate vaccine and Bexsero[®] vaccine from Visit 1 to Visit 4, but received at least one dose of routine vaccines from Visit 1 to Visit 4, the actual vaccination group is “Other”

The safety analysis tables will not present data for ‘Other’ group, and the safety data for ‘Other’ group will be listed only.

Safety data recorded for a vaccine received out of the protocol design will be excluded from the analysis (and listed separately).

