12.2.2.5 Safety Analysis Set for Vaccination at 12-13 Months of Age (SafAS4)

The SafAS4 for vaccination at months of age is defined as those subjects who have received at least one dose of the study vaccines at Visit 4 around 12 to 13 months of age and have any safety data available. All subjects will have their safety analyzed after Visit 4 dose according to the vaccine(s) they actually received at Visit 4.

The subjects received at least one dose of study vaccines but out of the planned vaccination schedule at Visit 4 will be classified to “Other” group. The safety analysis tables will not present data for ‘Other’ group at Visit 4, and the safety data for ‘Other’ group at Visit 4 will be listed only.

Safety data recorded for a vaccine received out of the protocol design at Visit 4 will be excluded from the analysis (and listed separately).

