12.2.4 Populations Used in Analyses

Immunogenicity analyses will be primarily performed on the PPAS, including PPAS1, PPAS2 and PPAS3 (immunogenicity persistence analyses after infant vaccination will be performed on the PPAS2). Additional immunogenicity analyses will be performed for exploratory purposes on the FAS, including FAS1, FAS2 and FAS3 (immunogenicity persistence analyses after infant vaccination will be performed on the FAS2). In the FAS, subjects will be analyzed by the vaccine group to which they were randomized.

The safety analysis will be performed on the SafAS, including SafAS, and SafAS1 through SafAS4. Subjects will be analyzed according to the vaccine(s) they actually received.

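### Rule 3 of the overall safety set assigns by randomised group although the set is as-treated, leaving some mis-vaccinated Group 3 infants with no group and keeping Group 1 infants not co-vaccinated at Visit 4 in Group 1

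*Protocol*

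**What the plan says.** Section 12.2.2.1 of the protocol sets the basis of the overall any-dose safety set (SafAS): "All subjects will have their safety analyzed after any dose according to the vaccine received from Visit 1 (2 months) to Visit 4". Section 12.2.4 repeats the principle for every safety set: "Subjects will be analyzed according to the vaccine(s) they actually received".

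Five rules then apply in order:

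1. "If one subject received both MenACYW conjugate vaccine" and Bexsero at Visit 4, the infant is Group 1, whatever the randomised group.
2. An infant who completed only Visit 1 and had Bexsero there takes the randomised group.
3. For infants not given both vaccines at Visit 4, the rule reads "but received at least one dose of MenACYW from Visit 1 to Visit 4, the actual vaccination group is either", then names Groups 1 and 2 as the only outcomes. The choice between them is "based on the randomization group", even where the Visit 4 vaccine is known.
4. The condition here reads "Else if one subject did not receive MenACYW conjugate vaccine but received at least one dose of Bexsero"; one such dose at any of the four vaccination visits makes the infant Group 3.
5. For an infant given neither MenACYW nor Bexsero, the rule reads "but received at least one dose of routine vaccines from Visit 1 to Visit 4, the actual vaccination group is", and the class it names is 'Other', which is listed and not tabulated.

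Section 12.2.2.5 groups the Visit 4 set (SafAS4) "according to the vaccine(s) they actually received at Visit 4". It has its own listed 'Other' class for infants vaccinated off the planned schedule at that visit.

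**The concern.** Rule 3 calls its result the actual vaccination group but takes it from the randomisation. Two problems follow.

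First, the rules are incomplete. Rule 3 offers only Groups 1 and 2, so the randomised group of a Group 3 infant matches neither. Rules 4 and 5 exclude anyone who had MenACYW.

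Second, the rules treat errors in opposite ways. Under rule 1 any infant given both vaccines at Visit 4 moves into Group 1. Under rule 3 a Group 1 infant known to have had MenACYW alone at Visit 4 does not move out. The overall Group 1 column can therefore include infants who reached Visit 4 and were not co-vaccinated, although co-administration at that visit is what separates Groups 1 and 2.

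Such an error is conceivable. The Visit 2 steps in Section 5.1.4 list MenACYW without a split by group, while the Visit 4 steps are split. Contacting the IRT for vaccine assignment lowers the risk.

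**Working it through.** No stated figure depends on these rules, so the check is of their logic. Rules 1 to 5 were applied as an if/else-if chain with Visits 1 and 3 as planned, over:

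- randomised group: 1, 2 or 3;
- Visit 2: MenACYW plus routine vaccines, or routine vaccines only;
- Visit 4: both vaccines, MenACYW alone, Bexsero alone, or not done.

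That gives 3 × 2 × 4 = 24 combinations.

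**Completeness.** Among infants randomised to Group 3, MenACYW appears in 4 combinations through Visit 2 and in 2 more through Visit 4 only, so 6 in all.

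| Visit 2 | Visit 4 | Overall SafAS |
|---|---|---|
| MenACYW + routine | both | Group 1 (rule 1) |
| MenACYW + routine | MenACYW alone | no group |
| MenACYW + routine | Bexsero alone | no group |
| MenACYW + routine | not done | no group |
| routine | both | Group 1 (rule 1) |
| routine | MenACYW alone | no group |

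Four of the 6 meet the condition of rule 3 and have no outcome.

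**Consistency with SafAS4.** Section 12.2.2.5 gives no mapping from vaccines to groups, so two readings are shown. Reading A maps by vaccine given (both = Group 1, MenACYW alone = Group 2, Bexsero alone = Group 3). Reading B takes the planned schedule to be the infant's own, so any Visit 4 error is 'Other'. Visit 2 is correct in every row.

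| Randomised | Given at Visit 4 | Overall SafAS | SafAS4, A | SafAS4, B |
|---|---|---|---|---|
| 1 | MenACYW alone | Group 1 | Group 2 | Other |
| 1 | Bexsero alone | Group 1 | Group 3 | Other |
| 2 | Bexsero alone | Group 2 | Group 3 | Other |
| 3 | MenACYW alone | no group | Group 2 | Other |
| 2 or 3 | both | Group 1 | Group 1 | Other |

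The first four rows disagree under either reading. The last row disagrees only under B.

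**Size.** With planned enrolment of 160 in Group 3 and 320 in Group 1, one infant is 1/160 = 0.6% or 1/320 = 0.3% of its column.

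**The repair, on the same 24 combinations.** Under the rewording set out in the fix, 8 assignments change:

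- 2 go from Group 1 to Group 2 (Group 1 infants given MenACYW alone at Visit 4, with or without MenACYW at Visit 2);
- 2 go to 'Other' (a Group 1 or Group 2 infant given MenACYW at Visit 2 and Bexsero alone at Visit 4);
- 4 go from no group to 'Other' (the Group 3 cases above).

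All 24 then have a class, and no MenACYW recipient is in Group 3.

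**The case against.** Several points on the other side stand.

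- Groups 1 and 2 have the same schedule through Visit 3. For an infant who leaves before Visit 4, the randomised group is the only way to tell them apart. Rule 3, however, is not limited to such infants.
- Section 12.2.2 deliberately separates by-visit from any-dose grouping, so some difference between SafAS and SafAS4 is intended. That does not excuse an undefined outcome, or an assignment by randomisation where the Visit 4 vaccine is known.
- Section 12.1 leaves conventions to the SAP. It also requires the SAP to accord with the protocol, and this rule is already written in the protocol.

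A reader might infer that the infant's events would appear in no table and no listing, so that an SAE or AESI could be lost. The documents do not support that. Sections 12.2.2 and 12.2.2.1 list separately the data for a vaccine received outside the protocol's design. That sentence assigns no group, but it does provide a listing. SafAS2 and SafAS4 each have a listed 'Other' class. Section 10.1 requires every SAE to be reported within 24 hours, Section 9.3.2.3.4 handles AESIs as SAEs, and Section 11.2 reconciles the safety and clinical databases.

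A reader might also infer that a Group 1 infant given MenACYW alone at Visit 4 is certainly Group 2 in SafAS4. Section 12.2.2.5 does not say so, and 'Other' is equally open.

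**Conclusion.** The point holds as a drafting error of small size. Rule 3 is undefined for an infant randomised to Group 3 who had MenACYW and was not given both vaccines at Visit 4. It also contradicts the as-treated definition for a Group 1 infant given MenACYW alone at Visit 4. Neither conclusion depends on how SafAS4 is read.

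The consequence is confined to the group column of mis-vaccinated infants in the overall any-dose safety tables, which are descriptive and test no hypothesis. How many infants are affected cannot be stated, because the protocol gives no misallocation rate. The primary non-inferiority analysis runs on the per-protocol set and is not affected.

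**What to change.** Reword rules 3 and 5 of Section 12.2.2.1, keeping rules 1, 2 and 4:

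- Limit assignment by randomised group in rule 3 to infants randomised to Group 1 or 2 who received MenACYW but were given neither MenACYW nor Bexsero at Visit 4.
- Class infants randomised to Group 1 or 2 and given MenACYW alone at Visit 4 as Group 2.
- Make 'Other' (listed) the residual class for every remaining combination. This includes a Group 3-randomised infant given MenACYW who does not meet rule 1, and an infant given MenACYW earlier and Bexsero alone at Visit 4.

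Simply classing by the Visit 4 vaccine would not do. On reading A it would put an infant with MenACYW at Visit 2 and Bexsero alone at Visit 4 into Group 3, the group meant to be free of MenACYW.

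The cost is the rewording and a few lines of derivation code, best settled before database lock. The downside is that a few MenACYW-exposed infants would be listed and not tabulated in the overall set.

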5.1.4 Visit Procedures

Each visit may be conducted at the site (site visit) or at the subject's home (home visit). Study staff will contact the subject's parent / legally acceptable representative to confirm upcoming visits.

Visit 1 (Day 0): Inclusion, and Vaccination

- 1) Give the subject's parent / legally acceptable representative information about the study, obtain written informed consent, and give him / her a signed copy.
- 2) Check inclusion and exclusion criteria for eligibility.
- 3) Collect demographic data.
- 4) Obtain verbal medical history about the subject, including ongoing medication. Collect maternal prenatal immunization with pertussis vaccine ([Section 5.2.7](#)).
- 5) Conduct a physical examination as per standard of care.
- 6) Take the subject's temperature. If the temperature is $\geq 38^{\circ}\text{C}$, postpone vaccination until the condition is resolved.
- 7) Call the interactive response technology (IRT) system for randomization, allocation of subject number and vaccine assignment.

- 8) Review warnings and precautions to vaccinations.
- 9) Administer the following vaccines. Each vaccine should be administered in the assigned location and documented appropriately:
 - a) Bexsero[®]: inject deep IM into the anterolateral area of the thigh
 - b) Infanrix hexa[®]: inject deep IM into the anterolateral area of the thigh
 - c) Prevenar 13[®]: inject IM into the anterolateral area of the thigh
 - d) Rotarix[®]: administer orally per instructions in the package insert

If multiple vaccines are administered at a single visit, each vaccine should be administered at a different anatomic site. If vaccines are given in the same limb, the injection sites should be separated by 1 inch or more, so that any local reactions can be differentiated.

- 10) Keep the subject under observation for 30 minutes and record any adverse reaction in the source document.
- 11) Give the parent / legally acceptable representative a diary card (the diary card should match the number of injections given at this visit, 3 injections for all groups), a thermometer, and a ruler, and go over the instructions for their use. Instruct the parent / legally acceptable representative to retain the thermometer and ruler throughout the duration of the study. At each subsequent visit, confirm that the parent / legally acceptable representative has retained the thermometer and ruler, replace only as necessary.

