- 12) Remind the parent / legally acceptable representative to expect a telephone call 8 days after Visit 1.
- 13) Remind the parent / legally acceptable representative to notify the site in case of an SAE.
- 14) Complete the relevant case report forms (CRFs) for this visit.

Telephone Call 1 (8 days after Visit 1)

Note: If day 8 falls on a weekend or a holiday, the telephone call may be made on the following business day.

- 1) Record relevant information concerning the subject's health status on the telephone contact form. If an SAE, including an AESI occurred, follow the instructions in [Section 10](#) for reporting it.
- 2) Remind the parent / legally acceptable representative to do the following:
 - Complete the D0 to D07 pages of the diary card.
 - Complete the remaining pages of the diary card.
 - Notify the site in case of an SAE.

Visit 2 (30 [+14] days after Visit 1): Collection of Safety Information, Vaccination, and Blood Sample

- 1) Collect and review the diary card with the parent / legally acceptable representative, including any AEs, medications, or therapy that occurred since vaccination. If an SAE, including an AESI, has occurred, follow the instructions in [Section 10](#) for reporting it.
- 2) Measure temperature. If the temperature is $\geq 38^{\circ}\text{C}$, postpone vaccination until the condition is resolved.
- 3) Review temporary contraindications for blood sampling. Ensure the subject has not had any antibiotics within the previous 72 hours (3 days).
- 4) Collect 3 mL of blood from the subjects in Subset A (BL1) (see [Section 5.1.2](#) and [Section 5.1.3](#) for definition of Subset A and details of the sample schedule, and [Section 7.1](#) for detailed instructions regarding the handling of blood samples). All attempts should be made to obtain a blood sample; however, if the attempts are unsuccessful, the subject could continue in the study with all the study procedures including vaccination.
- 5) Review warnings and precautions to vaccinations.
- 6) Review contraindications to subsequent vaccinations and conditions for withdrawal.
- 7) Contact the IRT system for vaccine assignment.
- 8) Administer the following vaccines. Each vaccine should be administered in the assigned location and documented appropriately.
 - MenACYW conjugate vaccine: inject IM into the anterolateral area of the thigh
 - Infanrix hexa[®]: inject deep IM into the anterolateral area of the thigh

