5.2.7.3 Definitive Contraindications

Should a subject experience an anaphylactic or other significant allergic reaction to the previous dose of vaccine(s), the Investigator will discontinue vaccination.

The following AEs constitute absolute contraindications to subsequent vaccination with any of the study vaccines. If a subject should experience any of these events during the study, that subject is not to receive any additional study vaccines but should continue in the study and be followed up for safety only as per protocol.

MenACYW conjugate vaccine:

- 1) MenACYW conjugate vaccine should not be administered to anyone with a history of severe allergic reaction to any component of the vaccine or after previous administration of the vaccine or a vaccine containing the same components or constituents.
- 2) MenACYW conjugate vaccine should not be administered to anyone with a history of Guillain-Barré syndrome within 6 weeks after a previous dose of tetanus toxoid-containing vaccine, or a history of Arthus-type hypersensitivity reactions after a previous dose of tetanus toxoid-containing vaccine.

Bexsero[®]:

- 3) Hypersensitivity to the active substances or to any of the excipients.

Infanrix hexa[®]:

- 4) Hypersensitivity to the active substances or to any of the excipients, or formaldehyde, neomycin and polymyxin.
- 5) Hypersensitivity after previous administration of diphtheria, tetanus, pertussis, hepatitis B, polio or Hib vaccines.
- 6) Infanrix hexa[®] is contraindicated if the infant or toddlers has experienced an encephalopathy of unknown etiology, occurring within 7 days following previous vaccination with pertussis containing vaccine.

Prevenar 13[®]:

- 7) Hypersensitivity to the active substances, to any of the excipients, or to diphtheria toxoid.

Rotarix[®]:

- 8) Hypersensitivity to the active substance or to any of the excipients.
- 9) Children with rare hereditary problems of fructose intolerance, glucose-galactose malabsorption or sucrase-isomaltase insufficiency should not receive the rotavirus vaccine as this contains sucrose as an excipient.
- 10) Hypersensitivity after previous administration of rotavirus vaccines.
- 11) History of intussusception.
- 12) Subjects with uncorrected congenital malformation of the gastrointestinal tract that would predispose for intussusception.
- 13) Subjects with SCID disorder.

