6.5 Randomization and Allocation Procedures

On the day of Visit 1, subjects who meet the inclusion/exclusion criteria and whose parent / legally acceptable representative signs the ICF will be randomly assigned to Groups 1 through 3 in a 2:2:1 ratio, such that Group 1 will have approximately 320 subjects, Group 2 will have approximately 320 subjects, and Group 3 will have approximately 160 subjects.

Site staff will connect to the IRT system, enter the identification and security information, and confirm a minimal amount of data in response to IRT prompts. The IRT system will then provide the group assignment and subject number. The full detailed procedures for group allocation are described in the Operating Guidelines. If the subject is not eligible to participate in the study, then the information will only be recorded on the subject recruitment log.

Subject numbers that are assigned by the IRT system will consist of a 12-digit string (a 3-digit country identifier, a 4-digit study center identifier, and a 5-digit subject identifier). For example, Subject 826000100005 is the fifth subject enrolled in Center Number 1 in the UK (826 being the UK country code).

Subject numbers should not be reassigned for any reason. The randomization codes will be kept securely in the IRT system.

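### Rules 2 and 4 of the overall safety set, read literally, can place infants with the same Visit 1-only exposure in different groups, depending on whether they stay for safety follow-up

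*Protocol*

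**What the plan says.** The overall safety set in section 12.2.2.1 classifies infants by the vaccines they received from Visit 1 to Visit 4, using five rules in order. Four bear on this point.

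- Rule 1 gives Group 1 to anyone who had both MenACYW and Bexsero at Visit 4.
- Rule 2, "Else if one subject only completed Visit 1 and received" Bexsero at that visit, keeps the randomised group.
- Rule 3 keeps Group 1 or Group 2 by randomisation for an infant who "received at least one dose of MenACYW from Visit 1 to Visit 4" without having had both vaccines at Visit 4.
- Rule 4, "Else if one subject did not receive MenACYW conjugate vaccine but received at least one dose of" Bexsero, assigns Group 3 whatever the randomised group.

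On stopping vaccination, section 5.2.7.3 says that after a definitive contraindication "that subject is not to receive any additional study vaccines but should continue in the study and be followed up for safety only". Section 5.2.10, however, lists a definitive contraindication that is an AE or SAE among the reasons for early termination. Section 5.2.11 then asks sites to complete the scheduled safety follow-up of infants who terminated for such reasons.

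In section 5.1.4 the Visit 1 vaccines are common to all groups ("3 injections for all groups", plus oral Rotarix), and MenACYW first appears at Visit 2.

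**The concern.** After Visit 1 alone, exposure cannot tell the three groups apart. Rule 2 acknowledges this by falling back on randomisation. Rule 4, as worded, withdraws that fallback from an infant with exactly the same exposure if later visits were completed. Group membership then depends on what happened in follow-up after randomisation, and one documented route into that situation is an adverse event that stops vaccination.

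The move can go only from Groups 1 and 2 into Group 3, which is a quarter of their combined size. What is at stake is the between-group comparison in the any-dose summaries and in whole-trial summaries built on the overall set, such as SAEs and terminations. Events from a period when all groups were treated alike could appear unevenly distributed.

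**Working it through.** **Inputs from the protocol**

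- Group sizes (6.5): "such that Group 1 will have approximately 320 subjects, Group 2 will have approximately 320 subjects, and Group 3 will have approximately 160 subjects". This reproduces from 2:2:1 of about 800: 800 × 2/5 = 320, 800 × 2/5 = 320, 800 × 1/5 = 160. Groups 1 and 2 together: 640.
- Visit 1 vaccines identical in all groups; MenACYW from Visit 2 (5.1.4).
- Later visits have safety procedures that need no vaccination. Visit 2, for example, opens with "Collect and review the diary card with the parent / legally acceptable representative, including any AEs" (5.1.4).

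**Step 1: apply the rules literally**

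Take an infant who had the Visit 1 vaccines, including Bexsero, and no other study vaccine.

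| Randomised to | Leaves after Visit 1 | Stops vaccines, completes later safety visits |
|---|---|---|
| Group 1 | Group 1 (rule 2) | Group 3 (rule 4) |
| Group 2 | Group 2 (rule 2) | Group 3 (rule 4) |
| Group 3 | Group 3 (rule 2) | Group 3 (rule 4) |

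In the right-hand column, rule 1 fails because nothing was given at Visit 4. Rule 2 fails because more than Visit 1 was completed. Rule 3 fails because there was no MenACYW. Rule 4 therefore applies. The exposure is the same in both columns.

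**Step 2: size, for an assumed frequency**

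Let r be the fraction of infants who stop vaccination for an event after Visit 1 and stay in follow-up, taken as equal in all groups. The protocol gives no r.

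- Moved into Group 3: 640r
- Group 3's own: 160r
- Proportion shown in Group 3 for this category of event: (160r + 640r)/(160 + 640r) = 800r/(160 + 640r)
- Proportion shown in Groups 1 and 2 for the same category: 0

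| Assumed r | Moved (640r) | Group 3 shows | True proportion, each group |
|---|---|---|---|
| 0.1% | 0.64 | 0.8/160.64 = 0.50% | 0.1% |
| 0.25% | 1.6 | 2/161.6 = 1.24% | 0.25% |
| 0.5% | 3.2 | 4/163.2 = 2.45% | 0.5% |
| 1% | 6.4 | 8/166.4 = 4.81% | 1% |
| 2% | 12.8 | 16/172.8 = 9.26% | 2% |

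The ratio to the true proportion stays a little under five, because the 800 infants' events are all counted against about 160. The absolute count is less than one infant moved at r = 0.1% and about six at r = 1%.

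**Step 3: after the change**

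If rule 2 depends on vaccines received, both columns of the first table give the randomised group. No infant moves, and each group shows r.

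**The case against.** Several points on the other side are sound.

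- *Completed* is not defined in rule 2. The list classifies by vaccine received, so the phrase could mean that only the Visit 1 vaccination was completed. Rule 2 would then already keep these infants in their randomised group.
- Under sections 5.2.10 and 5.2.11 a site could record the infant as terminated after Visit 1 while still following for safety, and rule 2 could then apply. Section 5.2.7.3 speaks of continuing in the study but does not say that Visits 2 to 5 are completed.
- Analysing by vaccine received is the stated principle of section 12.2.2. Rule 4 responds to non-receipt of MenACYW for any reason, not specifically to an adverse event.
- The contraindications in section 5.2.7.3 are mostly rare, such as severe allergy, Guillain-Barré syndrome or encephalopathy. At r = 2%, 16 of 800 infants would have to stop after one visit and all stay.
- Safety is descriptive (12.1.3). The safety objectives in section 2.3 are tied to particular vaccination ages, which the per-visit sets serve.

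These points limit how certain and how large the effect is. They do not remove the inconsistency. On the first two, the infant's group would rest on how an undefined phrase is read or how a site fills in a form. On the third, the principle cannot separate the groups when the vaccines received are the same, which is why rule 2 exists.

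A reader might infer that the rules make MenACYW look safer by moving its reactions into the comparison group. The documents do not support that. The stopping event follows vaccines common to all groups and precedes any MenACYW dose.

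A reader might also take the zero for Groups 1 and 2 as describing the SAE or AESI tables. It describes only the category of infants who stopped after Visit 1 and stayed. Three of the four AESIs in section 9.3.2.3.4 (generalised seizures, Kawasaki disease, thrombocytopenic purpura) are not listed as definitive contraindications in section 5.2.7.3.

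**Conclusion.** The point stands as a minor inconsistency in a stated rule. On the literal wording, infants with identical exposure can be classified differently according to whether they complete later safety visits, and the only possible move is from about 640 infants into a group of about 160. Because it can follow from an adverse event, it can distort the descriptive any-dose and whole-trial comparison.

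It does not reach SafAS1, where a Visit 1 reaction is analysed by the vaccines given at Visit 1, and it does not touch the primary immunogenicity analysis.

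The conclusion rests on reading rule 2 as referring to visits rather than vaccinations, and on the infant being recorded as continuing rather than terminated. The percentages rest on an assumed r that is equal in all groups. They are illustrative only, and the real number is probably small.

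**What to change.** 1. In rule 2 of section 12.2.2.1, replace *only completed Visit 1* with *received study vaccines at Visit 1 only*, keeping the condition on Bexsero.
2. Limit rule 4 to infants who received further study vaccines at or after Visit 2 without MenACYW. Infants with a genuine Group 3 type of exposure still go to Group 3, and the narrowing leaves no one unclassified, since infants with Bexsero at Visit 1 only are caught by rule 2.
3. Reconcile sections 5.2.7.3, 5.2.10 and 5.2.11 on whether an infant with a definitive contraindication is recorded as continuing or as terminated. The sponsor should decide which record applies; the analysis group should not depend on it.

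The cost is a few phrases in the protocol and the matching derivation. No new data are needed.
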